3.2. Study Endpoints

3.2.1. Primary Study Endpoints

The primary endpoint will be proportion of subjects with clinical resolution of diarrhea without recurrence in subjects with R-CDI at 8 weeks (56 days) following FMT. Clinical resolution will be defined as follows:

- ≤ 4 stools per calendar day for the prior two days with no stool of Bristol stool scale type 7
- No additional stool tests with a positive EIA for *C. difficile* toxin since study enrollment
- No additional prescription or use of anti-CDI antibiotics (unless given for prophylaxis) since study enrollment
- No need for an additional FMT administration since study enrollment
- Subject is alive

3.2.2. Secondary Study Endpoints

Secondary endpoints include:

- All-cause mortality at 30- and 60-days following last FMT
- Colectomy or diverting ileostomy within 30 days after last FMT
- Cumulative days of hospitalization from enrollment until 30 days after FMT
- Cumulative days in intensive care unit from enrollment until 30 days after last FMT
- Bacteremia from enrollment until 30 days after last FMT
- Hospital admission within 60 days of discharge from index hospitalization

3.2.3. Primary Safety Endpoints

The primary safety endpoints will include:

- Frequency of solicited adverse events (AEs)

- Frequency of serious adverse events (SAEs)
- Frequency of AEs of special interest (AESIs)

See [section 9](#) for additional details on adverse event definitions.

3.2.3.1. Post-PMT Administration monitoring: Bedside for 60 Minutes

Safety endpoints for all routes of administration will include worsened abdominal pain, fever, tachycardia, and hypotension ([Section 3.2.1](#)). Safety endpoints for upper enteral delivery (i.e., PMT-002 or PMT-003) will include evidence of aspiration (including reduced oxygen saturation, tachypnea, or respiratory distress, as defined above).

3.2.3.2. Post-PMT Administration Follow-Up

Safety endpoints assessed at the 7-day follow-up and all subsequent follow-ups will include fever, diarrhea, nausea, and vomiting. Safety endpoints assessed at the 30-day, 56-day, 90-day, and 180-day follow-ups will include evidence of new metabolic disease, including hyperglycemia, thyroid disease, weight gain or loss.

4. Study Population and Duration of Participation

4.1. Inclusion Criteria

1. Second or greater episode of CDI (first or greater recurrence) within 12 months, with symptoms including bowel movement altered in frequency or consistency from baseline.
2. Stool positive for *C. difficile* toxin by EIA or toxin gene by NAAT within 60 days of enrollment.
3. At least one additional prior positive stool test for *C. difficile* within the prior 12 months (EIA or NAAT as above).
4. Age \geq 18 years.
5. Minimum of 72 hours of receipt of standard-of-care (vancomycin or fidaxomicin) antibiotic treatment for R-CDI prior to intervention.

4.2. Exclusion Criteria

1. Evidence of colon/small bowel perforation at the time of study screening
2. Goals of care are directed to comfort rather than curative measures.
3. Moderate (ANC < 1000 cells/uL) or severe (ANC < 500 cells/uL) neutropenia.
4. Known food allergy that could lead to anaphylaxis.
5. Pregnancy
 - a. For subjects of childbearing potential (ages 18 to 55), the subject must have a negative urine pregnancy test within 48 hours of consent and no more than 48 hours prior to first product administration
6. Meeting criteria for severe, severe-complicated/fulminant CDI within 24 hours of planned trial enrollment. We define severe or severe-complicated/fulminant CDI as any one of the following: (1) leukocytosis with peripheral WBC $\geq 15,000$ cells/mL; (2) hypotension with systolic blood pressure sustained < 90 mmHg for three or more hours or requiring pressors; (3) provider documentation of ileus or radiologic evidence of bowel dilation or megacolon;

(4) acute kidney injury with increase in baseline serum creatinine level by $\geq 50\%$ or new dialysis initiation; (5) serum lactate > 2.2 mmol/L; or (6) ≥ 3 systemic inflammatory response syndrome (SIRS) criteria (which include heart rate > 90 beats per minute, respiratory rate > 20 breaths per minute or $\text{PaCO}_2 < 32$ mmHg, temperature $> 38^\circ\text{C}$ or $< 36^\circ\text{C}$, $\text{WBC} > 12,000$ cells/uL, $< 4,000$ cells/uL, or $> 10\%$ immature (band) forms).

7. Receipt of FMT or enrollment in a clinical trial for FMT within the last 3 months.

4.3. Subject Recruitment

Because FMT is recommended therapy for R-CDI, potential subjects will be identified by active screening or referral from care providers within the University of Pennsylvania Health System (PennMedicine). Potential subjects' health records will be initially screened by a study team member to evaluate if the inclusion/exclusion criteria may be met. If a potential subject may meet inclusion/exclusion criteria, the potential subject (or their designated medical decision-maker) will be contacted in person or by telephone to discuss participation. If a potential is currently admitted to the hospital and the primary team was not the referring team, the study team will contact the subject's inpatient care team to ascertain whether the care team has any objection to the study team enrolling the potential subject. The potential subject (or their designated medical decision-maker) will be contacted to discuss participation. If the potential subject is eligible and wants to participate, informed consent will be obtained. At this time, subjects of childbearing potential (ages 18 to 55) will have a urine pregnancy test performed. If a urine pregnancy test is not able to be performed or if it is positive, the potential subjects will be excluded.

4.4. Duration of Study Participation

The subjects will participate in the study for 180 days (+/- 7 days) after the last administration of the PMT product. Study participation will conclude with the 180-day follow-up visit (in-person or by telephone).

4.5. Total Number of Subjects and Sites

Recruitment will be performed at one site with six participating PennMedicine University of Pennsylvania Health System locations: (1) the Hospital of the University of Pennsylvania (HUP), (2) Penn-Presbyterian Medical Center (PPMC), (3) Pennsylvania Hospital (PAH), (4) Lancaster General Hospital (LGH), (5) Chester County Hospital (CCH), and (6) PennMedicine Princeton Medical Center (PMPMC). Enrollment targets 300 subjects.

4.6. Vulnerable Populations

Children, fetuses, or neonates are not included in this research study because the gastrointestinal microbiome is significantly different between children and adults. Pregnant women will not be eligible to participate in this study due to unknown risks of FMT in pregnancy. Prisoners will be eligible to participate in this study. Disabled, economically- or educationally-disadvantaged persons will be eligible for enrollment. Vulnerable populations will be protected via the informed consent process, which ensures that enrolled subjects or subject-surrogates understand study risks and benefits. Vulnerable populations will be protected from coercion because there is no financial benefit to participation in the study.

5. Study Intervention

5.1. *Description*

Penn Microbiome Therapy suite of investigational products have been described previously in [Section 1.2](#). The product label will include (1) a unique dose identifier (and barcode), (2) the PMT formulation (PMT-001, PMT-002, or PMT-003), (3) a donor identifier, (4) the date of donation and dose processing, and (5) the expiration date.

5.2. *Intervention Regimen*

This study is a randomized, controlled, open label trial. Subjects will be screened to evaluate if they meet inclusion criteria for recurrent CDI. If eligible, subjects will participate in the informed consent process. Following informed consent, the route of administration will be determined by the ability of the subject to safely receive oral capsules, intragastric/duodenal/jejunal infusion, or enema, as determined by the subject's treating physician, and by subject preference. Subjects will then be randomized to one of two arms using stratified randomization by route of delivery: (1) a single administration of FMT developed from 40g of human stool, which contains 1×10^8 – 1×10^{12} anaerobic bacterial CFUs (single dose), versus (2) two administrations of the same FMT formulation administered within 24 hours of each other (double dose). Subjects randomized to receive double-dose FMT will receive two doses from the same donor (but not necessarily from the same manufacturing batch). If a subject is unable to take at least 50% of a dose, they will be permitted to opt to receive a different route of administration for one dose within 24 hours. Subjects randomized to the arm with a double dose will receive the second dose as long as they do not have bowel surgery in the interim. Subjects will be followed until 180 days after their last PMT dose. Any antibiotics prescribed as part of routine clinical care for CDI will be stopped 12–48 hours (target 24 hours) prior to the intervention.

5.3. *Receipt*

The prescribed formulation of the investigational product [PMT-001 (Enema), PMT-002 (Suspension) or PMT-003 (Capsule)] will be packaged on dry ice from the PMT manufacturing facility at the University of Pennsylvania. The time of release from frozen storage will be documented and included in PMT product packaging. PMT products will be delivered by study staff or courier in single doses. Upon receipt of the product by the Investigator, packaging (bags for PMT-001 and PMT-002; capsule containers for PMT-003) will be inspected for integrity, and product will be checked to ensure that it is still frozen and logged in the investigational product accountability log. The investigational product label will also be checked to ensure that the proper product is received, and to ensure that the product has not expired.

5.4. *Storage*

Investigational products are transported frozen on dry ice by courier or study staff to the clinical location. Investigational products are transported in containers labelled and maintained at a temperature in accordance with federal and local regulations for the transport of biological products.

At the clinical location, administration of PMT-001 or PMT-002 will be initiated within 180 total minutes of product release from frozen storage. At the clinical site, administration of PMT-003 will be initiated within 120 minutes of product release from frozen storage. The time of release from frozen storage will be included in PMT product packaging ([Section 5.3](#)).

PMT-001 and PMT-002 doses will be thawed at room temperature for 30-60 minutes prior to administration. The bag may be massaged during thawing. PMT-003 will remain on dry ice until the time of administration.

Any doses released from frozen storage but not administered within the allotted time (180 minutes for PMT-001 and PMT-002, 120 minutes for PMT-003) after release (e.g., due to delays in transport) will be destroyed. In such cases, eligible subjects will be offered another dose, and the release process will be re-initiated.

5.5. Preparation and Packaging

Preparation of the three investigational products [PMT-001 (Enema), PMT-002 (Suspension) and PMT-003 (Capsule)] will be performed at the PMT manufacturing facility at the University of Pennsylvania. PMT-001 and PMT-002 are packaged in EVA bags suitable for storage at < -70°C (target -80°C). PMT-003 is encapsulated within three nested gelatin capsules (sizes 00, 0, and 1), then packaged in an HDPE capsule container suitable for storage at < -70°C (target -80°C). The three investigational products will be packaged in single doses.

5.6. Blinding

Neither subjects nor investigators will be blinded.

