6.3.3. Follow-up 56 days

Subjects will be contacted by telephone or in-person at 56 days (+/- 7 days) after final FMT for an interview focused on the primary outcome and potential adverse events. Telephone versus in-person follow-up will be determined based on subject preference. (If subjects prefer to be seen in person, but have been discharged from the hospital, a clinic visit with a study team member will be arranged).

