6.3.5. End-of-study visit at 180 days

The study will conclude after subjects are contacted by telephone or in-person at 180 days (+/- 10 days) after final FMT for a final interview focused on potential adverse events. Telephone versus in-person follow-up will be determined based on subject preference. (If subjects prefer to be seen in person, but have been discharged from the hospital, a clinic visit with a study team member will be arranged).

Subjects will be permitted to initiate electronic communication with the study team, although planned follow up visits will be conducted by telephone or in person. The study team may reach out to subjects electronically if difficulties arise in reaching the subject by telephone in order to schedule visits, but study-related questions will not be asked electronically. Subjects will be classified as lost to follow up if at least three attempts are made at contact without success; however, medical record review will still be used to obtain follow up information on these subjects. If a subject is eligible and enrolled a second (or greater) time, then their subsequent follow up will be conducted according to the schedule set by their most recent enrollment, and any remaining follow ups from earlier enrollment(s) will not be performed.

6.4. *Rescue Therapy*

If a subject is thought to have a severe adverse event it will be recorded by the study team and the subject will be followed until resolution and referred to subject's primary clinical care team. In the case of an inadequate clinical response, the subject's primary clinical care team will be contacted, so that the subject can pursue treatment at their discretion. Regardless of rescue therapy used, subjects will continue to be followed until the end of the study.

6.5. *Unscheduled Visits*

Data collected from subjects who contact the study team (by telephone, electronically, or in-person) outside of the scheduled visits (as above) will be associated with the next scheduled study visit, as each study visit is intended to retrospectively cover the time period since the last study visit.

6.6. *Subject Withdrawal*

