Subjects who are discharged from the hospital prior to 7 days following their last FMT will be provided with a diary and thermometer to keep track of their temperature (once a day), stool frequency, and any emesis. This diary will be reviewed with subjects at their 7-day follow-up visit.

For the exploratory aim, immune phenotypic analysis using flow cytometry may be performed on a subset of subjects using whole blood collected for clinical purposes, which would otherwise be discarded. Blood will be collected from residual material available in EDTA ("purple top") vacutainer tubes already collected in the clinical laboratory.

7.7. *Efficacy Evaluations*

The primary outcome (time to resolution of R-CDI symptoms) will be assessed at 8 weeks (56 days) following the intervention. The criteria will be assessed via patient interview and electronic medical record review as per Section 3.2.1.

7.8. *Genetic Testing (only if applicable)*

No human genetic testing will be performed. For the exploratory aim, stool microbiome analysis will be performed on stool samples obtained as described in [Section 7.6](#). These stool samples would otherwise be discarded. This will involve sequencing of microbial nucleic acids. This will not involve human DNA sequencing and thus does not comprise genetic testing. Likewise, phenotyping of immune response via flow cytometry may be performed on a subset of subjects, using whole blood collected for clinical purposes that would otherwise be discarded. This will not involve human DNA sequencing and or genetic testing.

7.9. *Safety Evaluations*

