8.4.2. Efficacy Analysis

An intention to treat analysis will be performed for the primary outcome of clinical resolution of diarrhea without recurrence in subjects with R-CDI at 8 weeks following FMT. A logistic regression model will be used to compare the two study groups (single-dose versus double-dose) to detect superiority of a dose. A p-value (one-sided) of <0.2 will be considered significant. As above, the primary analysis will be stratified based on the most recent positive CDI test (NAAT versus EIA) prior to enrollment. Per protocol analysis will also be performed, based on received (rather than randomized) treatment.

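### The plan does not mask the day-56 interview or the endpoint scoring, although parts of the endpoint are self-reported or judged and an excess of about 7 cures per 135 (11 if two-sided) gives a positive result

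*Combined protocol and SAP*

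**What the plan says.** Section 5.6 consists of one sentence: "Neither subjects nor investigators will be blinded". On the assessment of the primary outcome, Section 7.7 says "The criteria will be assessed via patient interview and electronic medical record review as per Section 3.2.1". Section 6.3.3 sets the timing and mode, "Subjects will be contacted by telephone or in-person at 56 days (+/- 7 days) after final FMT", and describes the contact as being "for an interview focused on the primary outcome and potential adverse events". Mode follows the subject's preference. The plan does not say who conducts the interview, who reviews the record or who decides cure or failure.

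Section 3.2.1 defines clinical resolution by five components:

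- **Stools.** A limit of four per day, "for the prior two days with no stool of Bristol stool scale type 7".
- **EIA.** No further positive toxin EIA since enrollment.
- **Antibiotics.** No further anti-CDI antibiotics, with an exception for prophylaxis.
- **Repeat FMT.** "No need for an additional FMT administration since study enrollment". The criterion is need, not receipt.
- **Survival.**

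The symptom diary covers only the 7 days after the last FMT (3.1.4, 6.3.1), so no diary supports the stool answer at day 56. The study performs no laboratory evaluations of its own (7.4), so EIA results arise only from routine care. After an inadequate response the care team is contacted "so that the subject can pursue treatment at their discretion" (6.4).

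The decision rule in 8.4.2 is "A p-value (one-sided) of <0.2 will be considered significant". Section 8.3 bases its power on a two-sided chi-square test with type I error 0.2. Section 8.4.2 plans no breakdown of the endpoint by component.

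**The concern.** Open-label dosing may be unavoidable when one arm receives a second administration. It does not follow that the person who asks about stools at day 56, or who classifies a prescription as prophylactic, must know the arm. The plan leaves this open, so the interviewer and scorer may be the person who gave the dose or doses.

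The protocol also gives staff a reason to expect one arm to do better. Section 1.3 suggests that a greater stool mass might be clinically meaningful, and the Study Summary asks whether repeat dosing is superior. A small difference in how questions are put or borderline cases are classified would then tend to favor double dose. Because the threshold is lenient, a shift of a few subjects could decide the result. Without a component table, a reader could not tell whether a difference came from positive EIAs and deaths or from recalled stools and judged retreatment.

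**Working it through.** **Inputs (Section 8.3).** 300 enrolled, 10% lost, leaving 135 per arm: 45 EIA and 90 NAAT. Single-dose cure rates are 70% (EIA) and 50% (NAAT). The critical value is z = 0.8416 for one-sided 0.2 (8.4.2) and z = 1.2816 for two-sided 0.2 (8.3).

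**The plan's own figures.** A two-sided two-proportion normal test with unpooled variance, at 80% power, type I error 0.2 and a 50% reference rate, gives detectable rates of 0.7134 (45 per arm) and 0.6544 (90 per arm). Section 8.3 states 0.7133 and 0.6543. The figures reproduce, and only as a two-sided calculation; the one-sided rule of 8.4.2 is a different test.

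**Standard error of the stratified difference with no true effect.** The weights are 45/135 = 1/3 and 90/135 = 2/3.

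Variance = (1/3)² × 2 × 0.70 × 0.30/45 + (2/3)² × 2 × 0.50 × 0.50/90 = 0.001037 + 0.002469 = 0.003506. SE = 0.0592.

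**Excess cures needed for a positive result, 135 per arm.**

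- One-sided 0.2: 0.8416 × 0.0592 = 0.0498, and 0.0498 × 135 = 6.7, so 7. Check: (7/135)/0.0592 = 0.876, above 0.8416; (6/135)/0.0592 = 0.751, below it.
- Two-sided 0.2: 1.2816 × 0.0592 = 0.0759, and 0.0759 × 135 = 10.2, so 11. Check: (11/135)/0.0592 = 1.376, above 1.2816; (10/135)/0.0592 = 1.251, below it.

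A Mantel-Haenszel test stratified on NAAT/EIA gives the same counts (z = 0.88 at 7 and 1.39 at 11). With all 150 per arm the one-sided count is 8. If each stratum were tested alone under the one-sided rule, it would be 6 of 90 (NAAT) and 4 of 45 (EIA).

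**Illustration of bias.** Let b be the total differential misclassification in favor of double dose, with no true effect. The chance of declaring double dose superior is 1 − Φ(z − b/0.0592).

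| b (assumed) | Subjects of 135 | One-sided 0.2 | Two-sided 0.2 |
|---|---|---|---|
| 0 | 0 | 0.20 | 0.10 |
| 2 points | 2.7 | 1 − Φ(0.504) = 0.31 | 1 − Φ(0.944) = 0.17 |
| 3 points | 4.1 | 1 − Φ(0.335) = 0.37 | 1 − Φ(0.775) = 0.22 |
| 5 points | 6.8 | 1 − Φ(−0.003) = 0.50 | 1 − Φ(0.437) = 0.33 |

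The two-sided column counts only results in favor of double dose. Simulation of the stratified test (400,000 trials per setting) gives 0.21, 0.32, 0.38 and 0.51 one-sided, and 0.10, 0.17, 0.21 and 0.33 two-sided. The small departures from the formula reflect the discreteness of the counts.

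**What masking can reach.** The interviewer can affect the stool item. The scorer can affect the prophylaxis and need-for-FMT judgments. Neither can affect what a subject believes, whether a clinician prescribes, or whether an EIA is ordered. The share of b that masking would remove cannot be estimated from the documents.

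**The case against.** The strongest reply is that the bias figures describe a total, while the remedy addresses a part. Antibiotic prescriptions and repeat FMT are events that record review can check, and a leading question cannot create a prescription. The stool item has numeric limits, and it changes the result only in subjects who have not already failed on another component. Nothing in the documents shows that interviewing alone could move 3 to 7 subjects. Both arms receive active, guideline-recommended FMT, and Section 1.3 itself calls the difference in anaerobic CFUs marginal, so expectation effects may be small. Part of the sensitivity comes from the deliberate 0.2 threshold. All of this stands, and it is why the table is an illustration and not an estimate.

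A reader might infer three stronger things that the documents do not support:

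- **That every step is known to be unmasked.** Section 5.6 covers subjects and investigators. The rest is silence about who interviews and scores. The defect is that nothing prevents an interviewer or scorer from knowing the arm.
- **That an unsatisfied single-dose subject would simply obtain a second trial FMT and count as a failure.** Re-enrollment is possible (3.1.4), but exclusion 7 bars anyone with FMT in the last 3 months, which is beyond the day-56 window. Only FMT outside the trial remains, and that is open to both arms.
- **That masking would restore the nominal false-positive rate.** It would not, because subjects and treating clinicians remain unmasked.

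**Conclusion.** The point holds as a gap in the design that is inexpensive to narrow. The plan does not mask the day-56 interview or the scoring, and three items depend on self-report or a scorer's judgment: stools, the prophylaxis exception and need for FMT. The decision threshold is about 7 cures at 135 per arm under 8.4.2, or about 11 under 8.3; the two sections disagree on sidedness and should be reconciled.

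The counts rest on the cure rates, stratum sizes and 10% loss assumed in 8.3, and on a single stratified test. The inflated false-positive rates rest on an assumed size and direction of bias and include sources that masking cannot reach. They show that the result is sensitive to small bias; they are no evidence that such bias will occur.

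**What to change.** Keep dosing open label and make three changes, preferably before any outcome is assessed.

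1. **Sections 5.6 and 6.3.3.** Have the primary-outcome questions asked from a fixed script, where feasible by an existing study-team member who did not dose that subject and is not shown the arm. Telephone contact is already allowed, but the subject chooses the mode and may have met several of the team at earlier visits, hence the qualification.
2. **Section 7.7.** Derive success or failure by a fixed program from the recorded components. Where a judgment on prophylaxis or need for FMT is required, make it from record extracts with arm and number of doses removed.
3. **Section 8.4.2.** Report each endpoint component by arm.

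A sensitivity analysis that counts failure only with record-documented diarrhea or a positive test is not advisable. The study does no stool testing, so real relapses in subjects followed by telephone could be recoded as cures.

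The cost is some reassignment of interviews, a short script, preparation of the extracts and one table, with no new staff, visits or tests. Some subjects or records will reveal the arm, so bias is reduced rather than removed.
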